6.2.3 Cost-effectiveness analysis

If the intervention is found to be effective, cost-effectiveness and cost-utility analyses will be prespecified in a separate economic analysis plan and conducted by an Economist at the University of Otago Wellington.

Not for Public Circulation or Reproduction

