SALTS is a 14-week, two-arm, parallel randomised controlled trial. A two-week baseline period (weeks -2 to -1) will be followed by 12 weeks intervention (weeks 1 to 12) Three hundred and twenty six adults (163 per group) with high BP will be randomised in a 1:1 ratio to receive either the salt reduction intervention (SaltSwitch app + dietary salt substitute) or control (generic information about heart-healthy eating), stratified by ethnicity (Māori and non-Māori) and age (<55yrs and 55yrs+). Randomisation will take place at the end of the baseline phase (beginning of week 1). The primary outcome is 24-hour urinary sodium excretion (mg/day) estimated using a spot (casual) urine sample at week 12. Secondary outcomes are (1) urinary potassium excretion (week 12), (2) average systolic BP (week 12),

Not for Public Circulation or Reproduction

(3) sodium content per 100g of packaged food purchases (week 12), (4) the number of participants achieving BP control (<135/85 mmHg; week 12)[1], and (5) use and acceptability of the SaltSwitch app and dietary salt substitute (week 12). Serious adverse events will be recorded, and if the intervention is effective then cost-effectiveness and cost-utility analyses will also be completed. Both groups will complete home-based BP measures twice per day (morning and evening) in triplicate during weeks -1, 6 and 12; collect a spot (casual) urine sample at weeks -1 and 12; and scan barcodes of all packaged foods purchased for consumption in the home during the 2-week baseline, and during the 2 weeks at the end of intervention (weeks 11 and 12) using a tailored study smartphone application.

Study population and number of participants

Participants will be 326 free-living adults (18yrs+) with high BP who own a smartphone and are willing to do grocery shopping during the study period. A General Practitioner (GP), healthcare provider, or study staff will have confirmed that they have high BP, and \geq 80% will have a recorded systolic BP (SBP) of \geq 140 mmHg at screening. Individuals with high BP and on antihypertensive medication will be eligible since effects of dietary salt reduction are additional to drug therapy[2]. The majority of participants (\geq 70%) will reside in the Auckland region.

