However, SaltSwitch does not address discretionary salt added in cooking and at the table, which accounts for ~15% of dietary intakes (the remainder is found naturally in fresh foods)²¹; this need can be met with dietary salt substitutes, which are used in place of regular table salt. Dietary salt substitutes are gaining in popularity because they are higher in potassium and lower in sodium but have a similar taste and flavour, thus reducing BP without requiring a change to habitual discretionary 'salt' use. Dietary salt substitutes have been found to be acceptable and effective in reducing BP in China^{22, 23}, and evidence from a 2019 meta-analysis (n=21 RCTs) found using a salt substitute can lead to a significant reduction in systolic and diastolic BP (DBP) for both hypertensive and normotensive adults (overall reduction: -7.8 (-9.5 to -6.2) mm Hg and -4.0 (-5.2 to -2.7) mm Hg, respectively)²⁴. However, the overall quality of evidence in the 2019 review was considered low, and there were few studies (n=8/21) in high income countries where discretionary salt generally contributes a lower proportion of total salt intake (~15% vs. 76%²⁵)²¹. Nonetheless, salt substitutes hold promise for reducing sodium intakes because the population benefits far outweigh any risks²⁶, they are cheap, easy to use, include potassium, and act as a salient reminder of the importance of reducing dietary salt from all sources²⁷.

Not for Public Circulation or Reproduction

4. Objectives

The primary objective of this study is to determine the effects of a 12-week dietary salt reduction intervention (SaltSwitch app + dietary salt substitute) on urinary sodium excretion in adults with high BP.

The secondary objectives are to determine the effects of the dietary salt reduction intervention on: (1) urinary potassium excretion (week 12), (2) systolic blood pressure at week 12 (3) sodium content of packaged food purchases (weeks 11 & 12), (4) the number of participants achieving BP control (≤135/85 mmHg; week 12), and (5) use and acceptability of the SaltSwitch app and dietary salt substitute (week 12).

Additional objectives are to record serious adverse events, and if the intervention is found to be effective then cost-effectiveness and cost-utility analyses will also be completed.

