4.2 Secondary hypotheses

12-weeks intervention with the dietary salt reduction intervention (SaltSwitch smartphone app + dietary salt substitute) will, compared with control:

- Increase urinary potassium excretion
- Reduce systolic blood pressure
- Reduce the sodium content of packaged food purchases
- Result in a larger proportion of participants achieving BP control (≤135/85 mmHg)
- Be cost-effective

It is also anticipated that the SaltSwitch app and dietary salt substitute will be used frequently and be acceptable to participants.

Not for Public Circulation or Reproduction

5. Study Design

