5.17 Primary outcome measure

24-hour urinary sodium excretion (mg per day) estimated using a spot (casual) urine sample at week 12.

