5.18 Secondary outcome measures

- 1. Urinary potassium excretion (mg per day) at week 12
- 2. Average systolic BP at week 12
- 3. Sodium content (mg per 100g) of packaged food purchases (weeks 11 and 12)
- 4. The number of participants achieving BP control (≤135/85 mmHg; week 12)
- 5. Use and acceptability of the SaltSwitch app and salt substitute at week 12 (intervention group only)

Serious adverse events will also be recorded during the trial period. If the intervention is found to be effective cost-effectiveness and cost-utility analyses will also be conducted.

Not for Public Circulation or Reproduction

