6.2 Statistical analysis

Statistical analysis will be performed on an intention-to-treat (ITT) basis, using SAS version 9.4 (SAS Institute Inc. Cary NC, USA). All statistical tests will be two-sided at 5% significance level. Trial results will be reported according to CONSORT 2010 guidelines for parallel group randomised trials.

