6.2.4 Interim analysis

No interim analysis will be undertaken in this trial.

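### Section 6.2.3 makes the writing of the economic analysis plan, not only its conduct, wait for a positive trial result, so the plan would not be prespecified

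*Protocol*

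**What the plan says.** Section 6.2.3 of the protocol reads: "If the intervention is found to be effective, cost-effectiveness and cost-utility analyses will be prespecified in a separate economic analysis plan". It adds that an economist will conduct the analyses. The statistical paragraph in the section 1 overview repeats this.

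The same condition appears elsewhere. The objectives, in sections 1 and 4, class the economic work as additional: "if the intervention is found to be effective then cost-effectiveness and cost-utility analyses will also be completed". Section 5.18 places it after the five numbered secondary outcomes, not among them: "If the intervention is found to be effective cost-effectiveness and cost-utility analyses will also be conducted". Section 4.2, by contrast, lists "Be cost-effective" among the secondary hypotheses with no condition attached.

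Two other statements bear on the timing and the criterion. Section 6.2.4: "No interim analysis will be undertaken in this trial". Section 5.17 gives the primary outcome as "24-hour urinary sodium excretion (mg per day) estimated using a spot (casual) urine sample at week 12". The protocol does not say which outcome or criterion decides that the intervention is effective for this purpose.

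**The concern.** An analysis plan protects against selective choices only if it is fixed before the results can influence it. Here the protocol calls the economic analyses prespecified, yet starts the specification only once the trial is known to have worked. Whoever writes the plan would then have the sodium and SBP estimates available, and could choose which of them drives the cost-effectiveness result.

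The choice could matter. The intervention is aimed at sodium intake, but section 5.19 describes it as blood-pressure lowering, and SBP has its own hypothesis in 4.2. The questionnaires listed in 5.13 and 5.14 collect doctor and hospital visits but no utility instrument. I therefore assume that a cost-utility analysis would have to be built on one of the trial's effect estimates. The protocol does not describe the model, so this is an inference.

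A smaller problem is that a null trial would leave a stated secondary hypothesis unexamined, because the condition in the other sections would not be met.

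**Working it through.** There is no figure in 6.2.3 to reproduce, so the check is mainly a reading of the sections against one another.

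**Step 1: what the condition covers.** In 6.2.3 the *if* clause stands at the head of the sentence and governs two verbs, the prespecifying and the conducting. In 5.18 and in the objectives it governs only the carrying out of the analyses. The timing problem therefore comes from 6.2.3 and its copy in section 1.

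**Step 2: when the condition can be met.** Section 6.2.4 excludes an interim analysis, and the primary outcome is measured at week 12. A finding of effectiveness can come only from the final analysis.

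**Step 3: combine.** The plan is written if and after effectiveness is found (step 1), and effectiveness is found only at the final analysis (step 2). The plan therefore follows the results.

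**Step 4: what remains open at that point.** Section 5.18 lists several outcomes that could supply the effect. Urinary sodium and SBP are the obvious two. No section names one, so the choice would be made with both estimates in view.

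**Step 5: status of the hypothesis.**

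| Place | Status of cost-effectiveness |
|---|---|
| 4.2 | Secondary hypothesis, unconditional |
| Sections 1 and 4, objectives | Additional objective, conditional |
| 5.18 | Outside the five numbered outcomes, conditional |
| 6.2.3 | Plan and analysis both conditional |

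Section 4.2 is the exception.

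**Step 6: does anything else in the trial depend on this?** The sample size does not. With 0.33 SD, two-sided 5% and 80% power, the t-test calculation gives 146 per group. Then 146 / (1 − 0.10) = 162.2, which rounds up to 163 per group and 326 in total, as section 6.1 states. No economic quantity enters this calculation.

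**Step 7: how much the unstated trigger could matter at most.** Section 6.2 says: "All statistical tests will be two-sided at 5% significance level". Effectiveness means benefit, so only the favourable 2.5% tail counts. If there were no true effect on any outcome:

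- Trigger is the primary outcome only: 2.5%.
- Trigger is any of the primary and the four between-group secondary outcomes, independent: 1 − 0.975^5 = 11.9%.
- The same five with a common correlation assumed at 0.5: 9.1%. At 0.8: 6.4%.

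The correlations are assumptions. The last two lines need the any-of-five reading, which is examined under the objection.

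**The case against.** The case against the point has real weight.

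- **A separate plan is promised.** The effect input, model and perspective normally belong in it, and their absence from the protocol is no error. This stands. The fault is only when the plan is written.
- **Running an economic evaluation only if the treatment works is a normal use of resources.** This also stands. The fix keeps that condition on the conduct.
- **The ordinary reading of effectiveness is benefit on the primary outcome.** There is one primary objective, one primary hypothesis and one powered outcome. The undefined trigger alone would be no more than missing detail. This stands, and the definition is worth adding only because the sentence is being rewritten anyway.
- **The consequence is small.** The economic work is an additional objective, outside the numbered outcomes. This stands and sets the severity.

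A reader might infer more than the protocol supports:

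- **That any positive outcome can start the economic analysis**, so that the 6.4% to 11.9% in step 7 is its false-trigger rate. No section says a secondary outcome can do so. Those figures bound a possible reading and do not describe the plan. Two-sided rates would be higher still, but they would count significant harm as effectiveness.
- **That the treatment contrast is unspecified.** "SALTS is a 14-week, two-arm, parallel randomised controlled trial". Two arms give one contrast. What is unnamed is the outcome.
- **That analysing only after significance inflates the effect used.** This is true of any analysis run only after significance. It would remain after the plan is dated correctly, so it is no argument for this change.

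The objection does not answer the timing. The text makes the plan itself conditional on the result.

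**Conclusion.** The point holds as a minor one. As worded, 6.2.3 and the matching sentence in section 1 have the economic plan written after the final results are known. It would then not be prespecified, and the effect input could be chosen with the results in view. The mismatch between 4.2 and the conditional statements elsewhere is real and also minor.

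The size of any resulting bias cannot be calculated, because the protocol gives neither the economic model nor its input. The primary analysis, its 5% level and the 326 participants are unaffected.

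The conclusion rests on a literal reading of 6.2.3. If the economic plan was in practice finalised before the outcome data were seen by allocation, the procedure is sound and only the wording needs correcting. The protocol does not show which is the case.

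**What to change.** Replace the sentence in 6.2.3, and its copy in section 1, with wording such as:

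*The economic analysis plan, including the outcome that supplies the effect estimate, will be finalised before database lock and before treatment allocation is merged with outcome data. The economic analyses will be conducted only if the intervention is effective, defined as a significant benefit (two-sided 5%) in the primary intention-to-treat analysis of week-12 urinary sodium excretion.*

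If SBP is to supply the effect, the economic plan should say so in advance. In 4.2, make the cost-effectiveness hypothesis subject to the same condition, or move it to the additional objectives.

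This is feasible, since section 5.6 already keeps allocations from the investigators during the study. It needs protocol wording and earlier work by the economist, with no new data or participants. The downside is drafting effort that goes unused if the primary result is null.

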6.2.4 Interim analysis

No interim analysis will be undertaken in this trial.

6.3 Data Management

The design and management of all databases associated with this trial (aside from the databases used for recruitment) will be undertaken by the study data manager [name] and statistician [name] in collaboration with the PI [name] and study co-investigators.

Not for Public Circulation or Reproduction

7. Ethical Approval and Consent

7.1 National ethics approval

Ethics approval was granted by the Health and Disability Ethics Committees (HDEC) on 17th February 2019 (Ref 18/NTB/239).

7.2 Scott committee approval

No medication will be administered as part of this study. Therefore, SCOTT approval is not required.

7.3 Informed consent

Maintenance of confidentiality and compliance with the Privacy Act will be emphasised to all study participants. Participation in the study will be entirely voluntary. A Participant Information Sheet (PIS) and Consent Form will be provided to all eligible potential participants. The consent form will include a question asking participants if they would be happy to be contacted up to two years after the study has finished, to assess longer term outcomes. Participants who do not consent to this question may still take part in the study. Electronic consent will be obtained at the baseline assessment within the study smartphone app. Prior to consent all participants will have had the opportunity to read the PIS and ask questions.

Not for Public Circulation or Reproduction

8. Assessment of Safety / Adverse Event Reporting

8.1 Adverse events

8.1.1 Definition of an adverse event

An adverse event (AE) is any untoward clinical occurrence in a participant which does not necessarily have a causal relationship with the treatment. An AE can therefore be any unfavourable and unintended sign, symptom, or disease temporally associated with the use of study treatment, whether or not it is considered related to the product. An AE will include any illness, sign, symptom, or clinically significant abnormality that has appeared or worsened during the course of the clinical trial, regardless of causal relationship to the treatment(s) under study.

AEs will not be recorded in this trial.

8.2 Serious adverse events

8.2.1 Definition of a serious adverse event

A serious adverse event (SAE) is any untoward clinical occurrence in a participant that does not necessarily have a causal relationship with the treatment. SAEs are those that result in: death, are life threatening (defined as an event in which the participant was at risk of death at the time of the event; it does not refer to an event which hypothetically might have caused death if it were more severe), require hospitalisation or prolongation of hospitalisation, cause persistent or significant disability/incapacity, result in congenital abnormality, are an important medical event (defined as a medical event(s) that may not be immediately life-threatening or result in death or hospitalisation but may jeopardise the subject/subject or may require intervention (e.g. medical, surgical) to prevent one of the other serious outcomes listed in the definition above).

SAEs will be recorded in this trial.

8.2.2 Contact for notification of serious adverse events

Participants will be informed on the PIS and consent form that they will be asked to report any SAEs that occurred during the study period, at the end of the study. The RA will report all SAEs immediately to the PI and PM who will then report them in the form of a safety update to HDEC, on a quarterly basis. The PI will have the overall responsibility of ensuring that all events are reported to the regulatory authorities in the appropriate timeframes and that the process is not breached.

8.3 Reporting safety information

As the SaltSwitch smartphone app and dietary salt substitute are considered low risk, SAEs will not be collected in real time, and data for participants experiencing SAEs will not be removed from the study. All SAEs will be recorded on the follow-up questionnaire within the study smartphone app and if necessary will be follow-up with a phone call to ensure completeness and accuracy of SAE information. If known, the name of the underlying illness or disorder (i.e. the diagnosis) will be recorded, rather than its individual symptoms. All reported SAEs will be assessed within 24hours by an authorised medical representative: [name] (or delegate) will determine whether the AE is an SAE.

Not for Public Circulation or Reproduction

8.4 Unblinding

Participants will not be blinded to receipt of the dietary salt reduction intervention. The study investigators will have no access to treatment allocations during the study. If unblinding is required this will be undertaken by an independent researcher.

8.5 Data safety and monitoring

Ellenburg et al. (2002) provide guidelines for deciding whether or not to establish a Data Safety and Monitoring Committee (DMC) for a trial. They propose that if two or more of the following criteria are met then a DMC is required[39].

- The trial is intended to provide definitive information about the effectiveness and/or safety
 of a medical intervention.
- 2. There are prior data to suggest that the intervention being studied has the potential to induce potentially unacceptable toxicity.
- 3. The trial is evaluating mortality or another major endpoint such that inferiority of one treatment arm has safety as well as effectiveness implications.
- 4. It would be ethically important for the trial to stop early if the primary question addressed has been definitively answered, even if secondary questions or complete safety information were not fully addressed.

The SALTS trial does not meet two or more of the above criteria. Consequently, a DMC will not be established for the trial.

Not for Public Circulation or Reproduction

9. Relevance to Health

High BP alone accounts for 8.3% of health loss in New Zealand (NZ)[10] and is a major risk factor for cardiovascular disease (CVD). One in five NZ adults currently has high BP, 17% take BP-lowering medication, and ~172,000 are living with CVD.[16] Cardiovascular disease is the leading cause of health loss for NZ males and the second ranked cause for NZ females, accounting for 10% and 6% of health loss respectively[10]. Furthermore, the burden of CVD is disproportionally attributed, with Māori and Pacific peoples suffering a greater proportion of the burden, particularly in the younger age groups (35 to 50 years)[17]. In 2006, CVD was estimated to account for 17.5% of the total national disease burden, with coronary heart disease (CHD) the leading specific cause of health loss accounting for 9.3% of disability adjusted life years (DALYs) lost by the population[10]. The costs of CVD to the healthcare system are also substantial; in 2011/12, hospitalisations for IHD cost \$228 million, for stroke \$67 million, and for high BP, \$6 million[18].

However, a considerable amount of CVD risk is potentially modifiable by reducing dietary salt intake[19], and in NZ there is substantial room for improvement; salt intake ranks as the second largest contributor to health loss[10], and our current population salt intake is ~40% higher than WHO recommendations (~8.4g (3,373mg sodium)/day compared with 5g (2,000mg sodium)/day, respectively)[21]. Further, despite being a signatory to the global 2013 WHO target to reduce population salt intake by a relative 30% towards 5g per day by 2025.[20], we do not (in contrast to 75 other countries internationally) have a government-led national salt reduction strategy. The Heart Foundation has worked with food manufacturers to reduce salt in low cost, high volume foods such as bread, but the trajectory of change to date suggests NZ will fall far short of realising our 2025 WHO commitment[14]. Therefore, more effective, scalable salt reduction interventions such as that being tested in the SALTS study (SaltSwitch app + dietary salt substitute) are urgently needed.

This research directly addresses four of the 10 key targets for NCDs were set by member nations at the 2012 World Health United Nations Assembly: (1) 25% relative reduction in overall mortality from CVD, cancer, diabetes or chronic respiratory disease; (2) 25% relative reduction in prevalence of raised BP; (3) 30% relative reduction in mean adult population intake of salt, with the aim of achieving recommended level of less than 5g/day; and (4) a minimum of 80% availability of affordable, quality-assured essential NCD medicines and technologies in public and private sectors[40]. Further, this research has the potential to reduce health inequalities. Māori, Pacific and those from lower socio-economic groups have similar dietary salt intakes to the general population[21] but are more likely to be affected by CVD than non-Māori, non-Pacific and those from higher socio-economic groups. With lower-cost smartphones being available to the market, the fact that the SaltSwitch app, once downloaded, does not require Wi-Fi or data to work, and the cheap cost of the dietary salt substitute, it is possible that this intervention could adequately reach Māori, Pacific and lower socio-economic groups. If found to be effective the intervention package being tested in the SALTS trial could be rolled out nationally at a relatively low cost.

Not for Public Circulation or Reproduction

10. Dissemination of Results

